10.0 CRITERIA FOR EVALUATION AND ENDPOINT ANALYSIS

This study will use the RECIST 1.1 guidelines. (39)

10.1 Measurability of Lesions

a. **Measurable disease**

Measurable disease is defined differently for lymph nodes compared with other disease and will be addressed in a separate section below.

1. Lesions that can be accurately measured in at least one dimension (longest diameter to be recorded) as ≥ 2.0 cm by chest x-ray, by ≥ 1.0 cm with CT or MRI scans, or ≥ 1.0 cm with calipers by clinical exam. All tumor measurements must be recorded in decimal fractions of centimeters (or millimeters).

The defined measurability of lesions on CT scan is based on the assumption that CT slice thickness is 0.5 cm or less. If CT scans have slice thickness greater than 0.5 cm, the minimum size for a measurable lesion should be twice the slice thickness.

2. **Malignant lymph nodes** are to be considered pathologically enlarged and measurable if it measures ≥ 1.5 cm in **SHORT AXIS** (greatest diameter perpendicular to the long axis of the lymph node) when assessed by scan (CT scan slice recommended being no greater than 0.5 cm).

- b. **Non-measurable disease:** All other lesions (or sites of disease), including small lesions (longest diameter < 1.0 cm or pathologic lymph nodes with ≥ 1.0 cm to < 1.5 cm short axis), are considered non-measurable disease. Bone lesions, leptomeningeal disease, ascites, pleural/pericardial effusions, lymphangitis cutis/pulmonitis, inflammatory breast disease, and abdominal masses (not followed by CT or MRI), are considered non-measurable as are previously radiated lesions that have not progressed.

c. **Notes on measurability**

1. For CT and MRIs, the same type of scanner should be used and the image acquisition protocol should be followed as closely as possible to prior scans. Body scans should be performed with breath-hold scanning techniques, if possible.
2. PET-CT: At present, the low dose or attenuation correction CT portion of a PET-CT is not always of optimal diagnostic CT quality for use with RECIST measurements. However, if the site can document that the CT performed as part of a PET-CT is of identical diagnostic quality to a diagnostic CT, then the CT portion of the PET-CT can be used for RECIST measurements and can be used interchangeably with conventional CT.
3. Ultrasound: Ultrasound is not useful in assessment of lesion size and should not be used as a method of measurement.
4. Cystic lesions that meet the criteria for radiographically defined simple cysts should not be considered as malignant lesions (neither measurable nor non-measurable) since they are, by definition simple cysts.

5. If a target lesion becomes very small some radiologists indicate that it is too small to measure. If the lesion is actually still present, a default measurement of 0.5 cm should be applied. If the radiologist believes the lesion has gone, a default measurement of 0.0cm should be recorded.

10.2 Objective Status at Each Disease Evaluation

Objective Status is to be recorded at each evaluation. All measurable lesions up to a maximum of 2 lesions per organ 5 lesions in total, representative of all involved organs, should be identified as *target* lesions at baseline. All other lesions (or sites of disease) including any measurable lesions over and above the 5 target lesions should be identified as *non-target* lesions. Measurements must be provided for target measurable lesions, while presence or absence must be noted for non-target measurable and non-measurable disease.

For studies that use disease progression as an endpoint, whole body scanning at specific intervals is necessary to determine that progression is NOT present outside of the "target" areas. Therefore, in these studies it is not acceptable to image only the "target" areas of the body in follow-up scans. For study-specific imaging requirements, see the Study Calendar in [Section 9.0](#).

- a. **Complete Response (CR):** Complete disappearance of all target and non-target lesions (with the exception of lymph nodes mentioned below). No new lesions. No disease related symptoms. Any lymph nodes (whether target or non-target) must have reduction in short axis to < 1.0 cm. All disease must be assessed using the same technique as baseline.
- b. **Partial Response (PR):** Applies only to patients with at least one measurable lesion. Greater than or equal to 30% decrease under baseline of the sum of appropriate diameters of all target measurable lesions. No unequivocal progression of non-measurable disease. No new lesions. All target measurable lesions must be assessed using the same techniques as baseline.
- c. **Stable:** Does not qualify for CR, PR, Progression or Symptomatic Deterioration. All target measurable lesions must be assessed using the same techniques as baseline.
- d. **Progression:** One or more of the following must occur: 20% increase in the sum of appropriate diameters of target measurable lesions over smallest sum observed (over baseline if no decrease during therapy) using the same techniques as baseline, as well as an absolute increase of at least 0.5 cm. Unequivocal progression of non-measurable disease in the opinion of the treating physician (an explanation must be provided). Appearance of any new lesion/site. Death due to disease without prior documentation of progression and without symptomatic deterioration (see [Section 10.2e](#)).

Notes regarding new lesions: FDG-PET imaging can complement regular scans in identifying new lesions according to the following algorithm.

1. Negative FDG-PET at baseline, with a positive FDG-PET at follow-up is a sign of progression based on a new lesion.
2. No FDG-PET at baseline and a positive FDG-PET at follow-up corresponding to a potential new site of disease must have a confirmation by anatomical assessment (e.g. CT, MRI, x-ray) as new site of disease to be considered progressive disease. In such a case, the date of progressive disease will be the date of the initial abnormal FDG-PET.

- e. **Symptomatic deterioration:** Global deterioration of health status requiring discontinuation of treatment without objective evidence of progression. Efforts should be made to obtain objective evidence of progression after discontinuation.
- f. **Assessment inadequate, objective status unknown.** Progression or symptomatic deterioration has not been documented, and one or more target measurable lesions have not been assessed or inconsistent assessment methods were used.
- g. Objective status notes:
 - 1. Non-measurable and non-target measurable disease do not affect Objective Status in determination of CR (must be absent--a patient who otherwise has a CR, but who has non-measurable or non-target measurable disease present or not assessed, will be classified as having a PR). However, non-measurable and non-target lesions are included in determination of progression (if new sites of disease develop or if unequivocal progression occurs in the opinion of the treating physician).
 - 2. An objective status of PR or stable cannot follow one of CR. Stable can follow PR only in the rare case that tumor increases too little to qualify as progression, but enough that a previously documented 30% decrease no longer holds.
 - 3. In cases for which initial flare reaction is possible (hypercalcemia, increased bone pain, erythema of skin lesions), objective status is not progression unless either symptoms persist beyond 4 weeks or there is additional evidence of progression.
 - 4. Lesions that appear to increase in size due to presence of necrotic tissue will not be considered to have progressed.
 - 5. For bone disease documented on bone scan only, increased uptake does not constitute unequivocal progression. However, increase in the soft tissue component of a lesion as measured by CT or MRI would constitute progression.
 - 6. Appearance of new pleural effusions does not constitute unequivocal progression unless cytologically proven of neoplastic origin, since some effusions are a toxicity related to therapy or other medical conditions. Increase in the size of an existing effusion does not constitute unequivocal progression, since the fluid status of the patient could alter the size of the effusion.
 - 7. If CR determination depends on a lesion for which the status is unclear by the required tests, it is recommended the residual lesion be investigated with biopsy or fine needle aspirate.

10.3 Best Response

This is calculated from the sequence of objective statuses.

- a. CR: Two or more objective statuses of CR a minimum of four weeks apart documented before progression or symptomatic deterioration.

- b. PR: Two or more objective statuses of PR or better a minimum of four weeks apart documented before progression or symptomatic deterioration, but not qualifying as CR.
- c. Unconfirmed CR: One objective status of CR documented before progression or symptomatic deterioration but not qualifying as CR or PR.
- d. Unconfirmed PR: One objective status of PR documented before progression or symptomatic deterioration but not qualifying as CR, PR or unconfirmed CR.
- e. Stable/no response: At least one objective status of stable/no response documented at least 6 weeks after registration and before progression or symptomatic deterioration, but not qualifying as anything else above.
- f. Increasing disease: Objective status of progression within 12 weeks of registration, not qualifying as anything else above.
- g. Symptomatic deterioration: Objective status of symptomatic deterioration within 12 weeks of registration, not qualifying as anything else above.
- h. Inadequate assessment, response unknown: Progression or symptomatic deterioration greater than 12 weeks after registration and no other response category applies.

10.4 Performance Status:

Patients will be graded according to the Zubrod Performance Status Scale.

POINT	DESCRIPTION
0	Fully active, able to carry on all pre-disease performance without restriction.
1	Restricted in physically strenuous activity but ambulatory and able to carry out work of a light or sedentary nature, e.g., light housework, office work.
2	Ambulatory and capable of self-care but unable to carry out any work activities; up and about more than 50% of waking hours.
3	Capable of limited self-care, confined to bed or chair more than 50% of waking hours.
4	Completely disabled; cannot carry on any self-care; totally confined to bed or chair.

10.5 Progression-Free Survival

- a. Primary Endpoint (Arms 1 and 2): From date of Step 2 Randomization to date of first documentation of progression or symptomatic deterioration (as defined in [Section 10.2](#)), or death due to any cause. Patients last known to be alive without report of progression are censored at date of last contact.
- b. Crossover Endpoint (Arm 3 only): From date of Step 3 Crossover Registration to date of first documentation of progression or symptomatic deterioration (as defined in [Section 10.2](#)), or death due to any cause. Patients last known to be alive without report of progression are censored at date of last contact.

10.6 Time to Death

From date of Step 2 Randomization to date of death due to any cause. Patients last known to be alive are censored at date of last contact.

11.0 STATISTICAL CONSIDERATIONS

All potentially eligible patients will be registered (step 1) and screened for BRAF, either passively (standard of care BRAF testing outside of trial in CLIA-compliant labs) or actively through consenting to be screened in this study. Patients who test positive for the V600E BRAF mutation are then eligible for randomization (step 2 registration) to treatment with irinotecan, cetuximab, and vemurafenib, or irinotecan and cetuximab. Patients randomized to the control arm (irinotecan and cetuximab) with disease progression during treatment are then eligible to cross over to treatment with vemurafenib in step 3 registration.

11.1 Accrual Goals

SWOG and the other adult oncology groups have no prior experience accruing this selected patient subset. By opening this study through CTSU, with support from ECOG-ACRIN, Alliance, and RNG, we are aiming for accrual of approximately 3 patients per month. The observed rate of accrual over the first 10 months was more than 4 patients per month. Thus, we anticipate enrolling 105 patients to have 94 eligible patients randomized in Step 2, and still expect 26 months of accrual.

The prevalence of V600E mutant BRAF is 5-7% (or 9-13% of KRAS wild-type tumors, given the mutual exclusivity of KRAS and BRAF). Some screening will be performed by sites that include BRAF in their standard of care testing, and for those pre-screened patients only retrospective confirmatory testing will be performed. Prior to opening the protocol, we estimated the screening sample size based on the following assumptions: the KRAS mutation rate is 40% and the BRAF mutation rate is 5.9% in mCRC; 60% of enrolled patients will come from sites that perform BRAF testing as part of the current standard of care; 85% of sites that do not perform BRAF testing will have KRAS testing results prior to considering a patient for study screening; the BRAF mutation rate is 9.8% in KRAS wild type patients; and 10% of screened patients will drop out and not enroll in the study. Based on these criteria, we estimated a need to perform primary central BRAF testing on approximately 440 patients. Forty-five of the first 70 screened patients were randomized. Of these 70 patients screened in 10 months of accrual, 43 had already been tested for the BRAF^{V600E} mutation and 27 needed central review. Based on these observed proportions, in total we will need to screen approximately 163 to randomize 105 patients, including about 63 patients needing central review.

11.2 Primary Analysis and Power Justification

The primary analysis of PFS among patients randomized to Arm 1 or Arm 2 will be conducted in all eligible patients according to the intent-to-treat principle, using the log rank test upon the observation of 88 PFS events. Patients will be stratified by prior treatment with irinotecan. There are no randomized second or third line studies that have reported outcomes with cetuximab and irinotecan specifically for the population of patients with BRAF mutations. However, a retrospective study of 75 patients with BRAF mutant tumors demonstrated progression-free survival of 2.4 and 2.3 months for second and third line regimens, respectively. (*in press, Clinical Colorectal Cancer*) Therefore, we estimate the median Progression-Free Survival (PFS) of patients treated with Cetuximab and Irinotecan to be 2.4 months (null hypothesis) in this study population. Assuming that the targeted agent offers an increase of 2.4 months in PFS for this population (HR 2.0), we will need 94 eligible patients, based on six months of follow-up, a two-sided type 1 error of 5% and 90% power.

An interim analysis will be performed when one-half of the events (approximately 44 PFS failures) have been observed (anticipated to occur when approximately 60% of accrual is reached). Evidence suggesting early termination would consist of a PFS hazard ratio > 1.0 comparing the experimental arm to the control arm, as estimated by a Cox regression model. This rule yields a 50% likelihood of terminating the study under the null hypothesis. Unless there are toxicity concerns, the study will not close during this interim assessment.

11.3 Other Analyses

Secondary endpoints will include overall survival, response, and toxicity. Distributions of overall survival in Arms 1 and 2 will be estimated using the method of Kaplan-Meier. The overall response rate (confirmed and unconfirmed, complete and partial) in each treatment arm will be assessed in the subset of patients with measurable disease. Assuming 90% (n=42 per arm) of patients will present with measurable disease, response rate can be estimated to within 16% (95% confidence interval).

Patients receiving at least one dose of drug on any arm will be included in the assessment of adverse events. Adverse event monitoring is conducted by the study chairs, disease committee chair, Adverse Event Coordinator and study statistician on an ongoing basis, with notification to the DSMC and CTEP should any concerns arise. Any events reported through the CTEP-AERS system are reported immediately, and reports are sent to the above group for all other AEs on a monthly basis. This trial will employ especially careful adverse event monitoring for the first 14 patients randomized to vemurafenib (Arm 2). Rates of serious toxicities will be compared between Arms 1 and 2 after 3, 6, and 14 patients are assigned to Arm 2 and have completed the first cycle, to inform discussions of protocol modification or early closure if required. Forty-seven eligible patients in each arm are sufficient to estimate the probability of a particular toxicity to within 15% (95% confidence interval). Any toxicity occurring with at least an 8% probability is likely (98% chance) to be seen at least once.

Patients progressing on Arm 1 will be provided the opportunity to cross over to vemurafenib treatment on Arm 3. Overall survival, response and PFS among patients who register to Arm 3 after disease progression will be summarized using descriptive statistics as described above.

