1.2 Secondary Objectives

- a. To evaluate the frequency and severity of toxicity associated with each of the treatment arms in this patient population.

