14.4 Data Submission Overview and Timepoints

a. ON THE SAME DAY AS STEP 1 INITIAL REGISTRATION:

For patients who have not yet undergone BRAF V600 testing, submit the following:

Tissue specimens for V600 BRAF testing directly to Moffitt Cancer Center as outlined in [Section 15.1](#).

Pathology report with specimens to Moffitt Cancer Center (see [Section 15.1](#))

b. WITHIN 7 DAYS AFTER STEP 1 INITIAL REGISTRATION:

Submit the **S1406** Onstudy Form

c. For patients who will not be randomized to a treatment arm, WITHIN 60 DAYS OF STEP 1 REGISTRATION:

Submit the pre-study plasma specimens (including pathology report) for Translational Medicine as described in [Section 15.3](#).

d. WITHIN 7 DAYS AFTER STEP 2 RANDOMIZATION:

Submit the following:

S1406 Randomization Eligibility Form

Baseline Tumor Assessment Form (RECIST 1.1)

Radiology reports from all scans performed to assess disease at baseline (NOTE: Upload reports via the Source Documentation: Baseline form found in the Randomization Disease Assessment Folder in Rave®.)

Pathology report (NOTE: Upload reports via the Source Documentation: Baseline form found in the Randomization Eligibility Folder in Rave®. This submission is in addition to the pathology report submission to Moffitt Cancer Center that is required by [Section 15.1](#))

Molecular testing report (NOTE: Upload reports via the Source Documentation: Baseline form found in the Randomization Eligibility Folder in Rave®.)

Fresh tissue for PDX (optional for patients at select institutions, see [Section 15.4](#)).

e. WITHIN 28 DAYS AFTER STEP 2 REGISTRATION (RANDOMIZATION):

Submit the tissue and plasma specimens (including pathology report) as described in [Section 15.0](#) (<http://swog.org/Members/ClinicalTrials/Specimens/STSpecimens.asp>).

f. WITHIN 14 DAYS AFTER EVERY CYCLE OF TREATMENT (INCLUDING BOTH ON INITIAL TREATMENT ARM AND CROSSOVER TREATMENT ARM):

Submit the following:

S1406 Treatment Form

S1406 Adverse Event Form

- g. For the first 14 patients (approximately) randomized to Arm 2, EVERY 14 DAYS WHILE ON TREATMENT:

Submit the **S1406** Adverse Event Form: In Rave, update the **date of most recent adverse event assessment** on the **Adverse Events: Assessment Form** at each assessment and then complete the **Adverse Events: Report Week 3-4**, accordingly, for each cycle of treatment.

- h. WITHIN 14 DAYS AFTER EVERY DISEASE ASSESSMENT (INCLUDING BOTH ON TREATMENT AND OFF TREATMENT PRIOR TO DISEASE PROGRESSION)*:

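### Per-patient toxicity percentages for Arms 1 and 2, shown side by side, cannot separate the toxicity of added vemurafenib from longer time on the same backbone; add time on treatment and a common-window table.

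*Combined protocol and SAP*

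**What the plan says.** Toxicity is the only objective listed under Section 1.2: "To evaluate the frequency and severity of toxicity associated with each of the treatment arms in this patient population". Section 11.3 defines who is counted ("Patients receiving at least one dose of drug on any arm will be included in the assessment of adverse events") and gives two design figures. The first is precision: "Forty-seven eligible patients in each arm" are "sufficient to estimate the probability of a particular toxicity to within 15% (95% confidence interval". The second is detectability: "Any toxicity occurring with at least an 8% probability is likely (98% chance) to be seen at least once".

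The one between-arm toxicity comparison that 11.3 names is the early safety review: "Rates of serious toxicities will be compared between Arms 1 and 2 after 3, 6, and 14 patients are assigned to Arm 2" and have finished their first cycle. For the end-of-study summary, I found no time window, exposure basis or time-to-event method in 11.3 or elsewhere in the protocol.

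Sections 7.2 and 7.3 continue treatment until a Section 7.6 criterion is met, the first of which is progression or symptomatic deterioration. Section 11.2 sets the control median PFS at 2.4 months and adds: "Assuming that the targeted agent offers an increase of 2.4 months in PFS for this population (HR 2.0". The Arm 2 median is therefore 4.8 months.

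**The concern.** If the trial succeeds as designed, Arm 2 patients may stay on treatment longer. They would then receive more cetuximab and irinotecan as well as vemurafenib, and have longer in which to record an event. A higher Arm 2 percentage could mean that vemurafenib adds toxicity, that patients had more months of the same backbone, or both. The percentages alone cannot say which.

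This matters most for events that start late or accrue. Section 3.1c reports hypomagnesemia in 55% of 365 cetuximab patients, with onset anywhere from days to months after starting. It matters little for acneiform rash, which the same section says usually appears in the first two weeks.

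Toxicity also bears on decisions. Section 11.2 lets toxicity concerns count at the interim look, and Section 11.4 sends the monitoring committee a report every six months, by which time exposure may already differ between arms.

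**Working it through.** **The plan's own figures.** The 95% half-width at p = 0.5 with n = 47 is 1.96 × √(0.25/47) = 14.3 points, which agrees with the stated 15. The chance of seeing an 8% toxicity at least once is 1 − 0.92^47 = 98.0%, as stated. Both are correct. The question is what the percentage measures.

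**Inputs.** Median PFS of 2.4 and 4.8 months comes from Section 11.2. Three things are assumed because the documents do not give them:
- Time on treatment is exponential and initially equal to PFS.
- The monthly rate L of a first toxicity is constant and the same in both arms, at 0.05, 0.10 or 0.20.
- Extra stopping for other reasons takes the values shown below.

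**Formula.** The stopping hazard is h = ln 2 / median: 0.289 per month in Arm 1 and 0.144 in Arm 2. Mean times 1/h are 3.46 and 6.92 months, a ratio of 2.0. The crude probability of at least one event on treatment is L/(L + h).

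**Full carry-over of the PFS effect, equal monthly toxicity:**

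| L per month | Arm 1 | Arm 2 | Gap (points) |
|---|---|---|---|
| 0.05 | 0.05/0.339 = 14.8% | 0.05/0.194 = 25.7% | 11.0 |
| 0.10 | 0.10/0.389 = 25.7% | 0.10/0.244 = 40.9% | 15.2 |
| 0.20 | 0.20/0.489 = 40.9% | 0.20/0.344 = 58.1% | 17.2 |

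**Sensitivity to other stopping**, with the extra hazard added to h:

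| Extra stopping per month | Ratio of mean time on treatment | Gap at L = 0.05 / 0.10 / 0.20 |
|---|---|---|
| 0.05, both arms | 1.74 | 7.6 / 11.2 / 13.6 |
| 0.10, both arms | 1.59 | 5.6 / 8.6 / 11.0 |
| 0.05, Arm 2 only | 1.49 | 5.7 / 8.2 / 9.8 |
| 0.10, Arm 2 only | 1.18 | 2.2 / 3.3 / 4.1 |

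Over all values of L, the maximum gap in the last row is 4.2 points. With 0.144 per month in Arm 2 only, the ratio is 1.0 and the gap disappears. If the true Arm 2 median were 3.6 months with no extra stopping, the maximum gap would be 10 points.

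**Common window.** Within w months of first dose the probability is L/(L + h) × (1 − e^(−(L + h)w)).
- For cycle 1 (w = 28/30.4), the gaps at the three rates are 0.3, 0.5 and 1.0 points.
- For cycles 1 and 2 (w = 56/30.4), L = 0.10 gives 13.1% versus 14.8%, and the gaps at the three rates are 0.9, 1.7 and 3.0 points.

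The model lets progression remove patients continuously. The Section 9 calendars place the first on-treatment CT or MRI in week 9, so the residual gap in a two-cycle window may be smaller still.

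**Check on a per-month rate.** Take an early toxicity with the same 88% incidence in both arms (the Section 3.1c figure for dermatologic events with cetuximab plus irinotecan), counted once per patient over mean treatment time. The rates are 0.88/3.46 = 0.25 and 0.88/6.92 = 0.13 per month. Arm 2 would look half as toxic when the incidence is identical.

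**The case against.** The quoted sentence is a precision statement, not an analysis specification. Objective 1.2a is descriptive and per arm, and the chance that a patient on a treat-to-progression regimen has a given toxicity answers it directly. It is also what patients and prescribers face. The only stated between-arm comparison comes after the first cycle, and no final test or decision rule uses the crude percentages. All of this stands. A reader might infer that the crude percentages are biased against vemurafenib; as estimates of per-arm frequency they are not. The difficulty arises only when a difference between them is attributed to the added drug.

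A reader might also infer that the design expects Arm 2 to be treated twice as long. The documents assume a doubling of PFS, not of treatment time, and they contain stopping routes that fall on Arm 2. Under Section 8.2e, a patient who must stop vemurafenib leaves all protocol treatment, whereas stopping only cetuximab or irinotecan does not end it. Under 8.3b, 8.3h and 8.3k, repeated nausea or vomiting, fatigue or rash eventually removes an Arm 2 patient altogether. For rash in Arm 1, only cetuximab stops. This also stands, so the 11-to-17-point figure is an upper one.

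Finally, a reader might conclude that arm comparisons should rest on windowed incidence and events per patient-month instead of the crude table. The 88% example shows why that goes too far: a rate per month misleads in the opposite direction for early toxicities. What the objection does not remove is that readers will compare the two columns, and the plan gives them nothing with which to judge exposure.

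**Conclusion.** The point holds as a limit on interpretation and a cheap improvement, not as an error in the estimate. With equal and constant monthly toxicity of 0.05 to 0.20, the crude gap is about 11 to 17 points if the PFS effect carries over fully to treatment time. It is about 6 to 10 points with 0.05 per month of extra stopping in Arm 2 only, and at most about 4 with 0.10. For toxicities confined to cycle 1 it is about 1 point or less.

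The upper figures are similar in size to the stated 15-point precision. That precision is for one arm, however; for a difference between two arms of 47 the half-width at p = 0.5 is 1.96 × √(2 × 0.25/47) = 20.2 points. The artefact is therefore a shift within considerable noise.

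The monthly rates and stopping hazards are assumptions, and the actual ratio of treatment times is unknown until the data are in, which is a reason to report it. The issue bears on later-onset events such as hypomagnesemia. Acneiform rash and the cycle-1 safety looks are little affected.

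**What to change.** In Section 11.3, keep the crude maximum-grade table as the main toxicity summary and add, by arm:

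1. Time on treatment, or cycles received.
2. Incidence of each toxicity within a common window of cycles 1 and 2, counted from first dose, with Arm 3 counted from the start of Step 3 treatment.

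State that any Arm 2 versus Arm 1 remark on the crude table is to be read together with these two. Events per patient-month may be shown only as a supplement for toxicities that accrue steadily, with a note that the rate understates Arm 2 for early-onset events.

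The cost is a few sentences and a few tables. Section 14.4f already requires the Treatment and Adverse Event Forms "WITHIN 14 DAYS AFTER EVERY CYCLE OF TREATMENT", so no new data are needed and enrollment, treatment and sample size are unchanged. The drawback is that the windowed figure omits late events; the retained crude table still shows them.
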